2.0 STUDY SUMMARY

Name of Sponsor: Takeda Development Center Americas, Inc.	Compound: Vortioxetine		
Title of Protocol: A Randomized, Double-Blind, Parallel Group, Placebo- and Active-Controlled, Phase 4 Study Evaluating the Effect of Vortioxetine 10 and 20 mg/day vs Paroxetine 20 mg/day on Sexual Functioning in Healthy Subjects	IND No.: 76,307	EudraCT No.: Not applicable	
Study Number: Vortioxetine-4001	Phase: 4		
Study Design: This is a phase 4, multicenter, randomized, double-blind, placebo- and active-controlled (paroxetine), 4-arm, parallel group, fixed-dose study comparing the effect of vortioxetine (10 and 20 mg once daily [QD]) vs paroxetine (20 mg QD) on sexual functioning after 5 weeks of treatment in healthy adult men and women. This outpatient study will be conducted at approximately 15 sites in North America. Men and women will be enrolled in approximately equal proportions (ie, 50% men and 50% women, overall). Enrollment will be capped for each sex when the enrollment target has been met for that sex stratum. Subjects will enter a Screening Period of up to 4 weeks. At Baseline (Day 0), eligible subjects will be equally (1:1:1:1) randomized to double-blind vortioxetine 10 mg, vortioxetine 20 mg, paroxetine 20 mg, or placebo and will be treated for 5 weeks. Randomization will be stratified by sex. Subjects allocated to vortioxetine 20 mg will initiate treatment at 10 mg/day for the first week. Subsequently, the dose will be increased to 20 mg/day and remain at 20 mg/day until study completion. Subjects allocated to vortioxetine 10 mg will initiate treatment at 10 mg/day and remain at 10 mg/day until study completion. Subjects allocated to paroxetine 20 mg will initiate treatment at 20 mg/day and remain at 20 mg/day until study completion. Subjects will be instructed to take their first dose of study drug the day after Baseline on Day 1, preferably in the morning. After randomization, subjects will be seen for weekly visits and receive a follow-up safety contact by telephone 2 weeks after the end of double-blind treatment. At the end of 5 weeks of treatment, or at early termination (ET), all subjects will abruptly discontinue study drug. Sexual functioning will be assessed at each study visit using the CSFQ-14 (primary variable). The PGI-I scale will be administered at each study visit except at Screening and Baseline. Signs of suicidal risk will be assessed at each study visit using the Columbia-Suicide Severity Rating Scale (C-SSRS) and the investigator's clinical judgment. Safety will be assessed throughout the study. A total of 6 sparse pharmacokinetic (PK) samples (trough samples) will be collected to measure plasma vortioxetine or paroxetine concentrations at Weeks 3, 4, and 5/ET (2 samples at each time point). A pharmacogenomic (PGx) blood sample for deoxyribonucleic acid (DNA) isolation will be collected predose at Baseline (Day 0), and 2 PGx blood samples for ribonucleic acid (RNA) isolation will be collected predose at Baseline (Day 0) and also at Week 5/ET (ie, 4 samples per subject).			
Primary Objective: 
• To evaluate the effect of vortioxetine (10 and 20 mg QD) vs paroxetine 20 mg QD on sexual functioning in healthy subjects after 5 weeks of double-blind treatment.			
Secondary Objectives: 
• To evaluate the effect of vortioxetine (10 and 20 mg QD) vs paroxetine 20 mg QD on sexual functioning in healthy subjects throughout the 5-week double-blind Treatment Period.• To evaluate the effect of paroxetine (20 mg QD) vs placebo on sexual functioning in healthy subjects throughout the 5-week double-blind Treatment Period.• To evaluate the effect of vortioxetine (10 and 20 mg QD) vs placebo on sexual functioning in healthy subjects throughout the 5-week double-blind Treatment Period.			

Additional Objectives: 
• To evaluate the effects of vortioxetine (10 and 20 mg QD) vs paroxetine (20 mg QD) on additional parameters of sexual functioning.• To evaluate the effect of vortioxetine (10 and 20 mg QD) and paroxetine (20 mg QD) vs placebo on additional parameters of sexual functioning.• To evaluate the subject's perception of sexual functioning.• To assess the treatment effect (vortioxetine, paroxetine, or placebo) on suicidal ideation and behavior.	
Safety Objective: 
• To evaluate the safety and tolerability of vortioxetine (10 and 20 mg QD) and paroxetine (20 mg QD) vs placebo.	
Subject Population: Healthy men and women aged 18 to 40 years, inclusive.	
Number of Subjects: Per each of 4 treatment arms: 88 Estimated total: 352	Number of Sites: Approximately 15 sites in North America
Dose Levels: 
• Vortioxetine 10 mg• Vortioxetine 20 mg• Paroxetine 20 mg• Placebo	Route of Administration: Oral
Duration of Treatment: Single dose QD for 5 weeks	Period of Evaluation: 5 weeks, plus a 2-week follow-up
Main Criteria for Inclusion: 
• The subject is a healthy male or female aged 18 to 40 years, inclusive.• The subject has been in a steady relationship for ≥ 3 months and plans to remain in that relationship for the duration of the study, and is currently sexually active (≥ 2 times per week). Note: Partners are not allowed to enroll in this trial.• The subject has a body mass index of 18 to 35 kg/m², inclusive, at the Screening and Baseline Visits.• If female, the subject has a regular menstrual cycle (note: amenorrhea resulting from hormonal contraceptives is not exclusionary).• The subject has normal sexual functioning, as defined by a CSFQ-14 total score >47 (men) or >41 (women) at the Screening and Baseline Visits.• If female, the subject taking allowed hormonal contraceptives is on a stable dose for ≥ 3 months prior to the Baseline Visit and continues on the stable dose for the duration of the study.	
Main Criteria for Exclusion: 
• The subject has a clinically significant unstable illness or a history of depression or any other psychiatric illness.• The subject is positive for hepatitis B surface antigen, anti-hepatitis C virus antibodies, or human immunodeficiency virus at the Screening Visit or has any known sexually transmitted diseases.• The subject has a known history of or currently has increased intraocular pressure or is at risk of acute narrow-angle glaucoma.• The subject has a significant risk of suicide according to the investigator's clinical judgment, or has made a suicide attempt at any time.• The subject has current sexual dysfunction, or a history of a diagnosis or treatment of sexual dysfunction.	

- The subject has had a surgical or medical procedure on reproductive/genitourinary organs (excluding uncomplicated cesarean section (C-section), vasectomy, and tubal ligation that do not impact sexual function).
- If female, the subject has polycystic ovarian syndrome.
- The subject has hypogonadism or has a free testosterone value outside the normal range at the Screening Visit that is indicative of hypogonadism.
- The subject has a history of or current alcohol or other substance abuse or dependence (according to the Diagnostic and Statistical Manual of Mental Disorders, Fourth Edition, Text Revised [DSM-IV-TR] criteria).
- The subject has habitual tobacco or other nicotine usage (equivalent to ≥ 10 cigarettes per day).

Main Criteria for Evaluation and Analyses:**Primary Endpoint**

- Change from Baseline in the CSFQ-14 total score difference for vortioxetine vs paroxetine after 5 weeks of treatment.

Secondary Endpoints

- Change from Baseline in the CSFQ-14 total score difference for vortioxetine vs paroxetine at each visit assessed.
- Change from Baseline in CSFQ-14 total score difference for paroxetine vs placebo at each visit assessed.
- Change from Baseline in CSFQ-14 total score difference for vortioxetine vs placebo at each visit assessed.
- Percentage of subjects meeting criteria for sexual dysfunction (ie, CSFQ-14 total score ≤ 47 for men and ≤ 41 for women) at any visit during the 5-week double-blind Treatment Period.
- Change from Baseline in CSFQ-14 subscales 5 dimensions (pleasure, desire/frequency, desire/interest, arousal/erection, and orgasm/ejaculation) and 3 phases of the sexual response cycle (desire, arousal, and orgasm/completion) at each visit assessed.

Additional Endpoints

- Percentage of subjects meeting criteria for sexual dysfunction (ie, CSFQ-14 total score ≤ 47 for men and ≤ 41 for women) at any 2 consecutive visits during the 5-week double-blind Treatment Period.
- Time to sexual dysfunction as assessed by the CSFQ-14.
- Percentage of subjects with a shift in the CSFQ-14 from normal (ie, CSFQ-14 total score > 47 for men and > 41 for women) at Baseline to abnormal (ie, CSFQ-14 total score ≤ 47 for men and ≤ 41 for women) at each visit assessed.
- Percentage of subjects showing decreased sexual function (ie, negative responders) according to the CSFQ-14 (ie, CSFQ-14 total score decrease from Baseline ≥ 3) at each visit assessed.
- PGI-I score at each visit assessed.
- C-SSRS at each visit assessed.

Safety Assessments

- Adverse events (AEs), vital signs, clinical laboratory tests, weight, and physical examinations.

Statistical Considerations:**Primary Analysis**

Mean change from Baseline in the CSFQ-14 total score difference for vortioxetine vs paroxetine after 5 weeks of treatment will be the primary endpoint. The primary analysis will be based on analysis of covariance (ANCOVA) using the last observation carried forward (LOCF) technique, with treatment, center, and sex as fixed factors, and baseline CSFQ-14 total score as covariate. The comparisons will be between each vortioxetine dose (10 or 20 mg) and paroxetine, and both statistical tests will be 2-sided. The Holm-Bonferroni method will be used to adjust for multiplicity and control the familywise type I error rate at a significance level of 0.05. If the smaller of the 2 p-values is < 0.025 , significance is obtained for the associated vortioxetine dose and the other dose will then be evaluated at a 0.05 significance level. Although vortioxetine will be compared with paroxetine in the primary analysis, paroxetine

will also be compared with placebo to validate the study.

Secondary Analyses

Change from Baseline in CSFQ-14 total score for vortioxetine vs paroxetine, paroxetine vs placebo, and vortioxetine vs placebo at each visit will also be analyzed using ANCOVA and LOCF, with treatment, center, and sex as fixed factors, and baseline CSFQ-14 total score as covariate. Similar analyses will also be performed for the male and female subgroups. Comparisons to placebo will be made at the significance level of 0.05 outside of multiplicity control.

The percentage of subjects meeting criteria for sexual dysfunction (ie, CSFQ-14 total score ≤ 47 for men and ≤ 41 for women) at any visit (using LOCF) during the double-blind Treatment Period will be analyzed by logistic regression, adjusting for baseline CSFQ-14 total score, sex, and treatment.

Change from Baseline in CSFQ-14 subscales 5 dimensions and 3 phases of the sexual response cycle will be analyzed at all visits using ANCOVA and LOCF similar to the primary analysis.

Additional Analyses

The percentage of subjects meeting criteria for sexual dysfunction (ie, CSFQ-14 total score ≤ 47 for men and ≤ 41 for women) at any 2 consecutive visits (using LOCF) during the double-blind Treatment Period will be analyzed by logistic regression, adjusting for baseline CSFQ-14 total score, sex, and treatment.

Time to sexual dysfunction as assessed by the CSFQ-14 will be analyzed using a Cox model with an exact method to handle ties, with treatment and sex as factors.

CSFQ-14 shift from normal (ie, CSFQ-14 total score > 47 for men and > 41 for women) at Baseline to abnormal (ie, CSFQ-14 total score ≤ 47 for men and ≤ 41 for women), and CSFQ-14 negative responders (decrease from Baseline in CSFQ-14 total score ≥ 3) will be analyzed at all visits by logistic regression, adjusting for baseline CSFQ-14 total score, sex, and treatment.

PGI-I will be analyzed by study visit using ANCOVA and LOCF, with treatment, center, and sex as fixed factors.

C-SSRS will be summarized by study visit for each treatment group using descriptive statistics.

Safety Analyses

AEs will be coded using the Medical Dictionary for Regulatory Activities (MedDRA) and will be summarized by system organ class and preferred term for the double-blind Treatment Period and the entire study. AEs that were reported more than once by a subject during the double-blind Treatment Period will be counted only once for that subject at the maximum severity.

Absolute values and changes from Screening/Baseline for clinical laboratory tests, vital signs, and weight will be summarized for each treatment group using descriptive statistics. Clinical laboratory test and vital sign results that are outside the normal ranges and potentially clinically significant will be flagged and tabulated. Physical examination findings will also be summarized for each treatment group.

PK Analysis

Plasma concentrations of vortioxetine and paroxetine will be presented in the data listings. A population PK analysis will only be conducted if deemed necessary. If this analysis is conducted, the results will be reported in a separate population PK report.

PGx Analysis

DNA samples may be used to understand the mode of action of vortioxetine, and RNA samples may be used for subsequent pathway analysis. Also, since PGx is an evolving science, many genes and their functions are not yet fully understood. Future data may suggest a role of some of these genes in drug response, which may lead to additional hypothesis-generating exploratory research and diagnostic development using stored samples.

Sample Size Justification:

Approximately 352 male and female subjects will be randomized to 4 treatment arms.

Assuming an SD of 8.5 for the change from Baseline in CSFQ-14 total score, a total of 352 male and female subjects (88 subjects per arm) is sufficient to achieve $\geq 80\%$ power to detect a difference of 4.0 for vortioxetine 20 mg vs paroxetine 20 mg or for vortioxetine 10 mg vs paroxetine 20 mg by a 2-sample t-test with a 0.025 2-sided significance level. Given the proposed Holm-Bonferroni method for multiplicity control, the power to achieve the significance for each vortioxetine dose is approximately 85%.

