Sexual functioning will be assessed at each study visit using the CSFQ-14 (primary variable). The PGI-I scale will be administered at each study visit except at Screening and Baseline. Signs of suicidal risk will be assessed at each study visit using the C-SSRS and the investigator's clinical judgment. Safety will be assessed throughout the study. A total of 6 sparse pharmacokinetic (PK) samples (trough samples) will be collected to measure plasma vortioxetine or paroxetine concentrations at Weeks 3, 4, and 5/ET (2 samples at each time point). A PGx blood sample for deoxyribonucleic acid (DNA) isolation will be collected at Baseline (Day 0), and 2 PGx blood samples for ribonucleic acid (RNA) isolation will be collected at Baseline (Day 0) and also at Week 5/ET (ie, 4 samples per subject).

The end of the study is defined as the date the last subject completes the Final Visit (Week 5). A schematic of the study design is presented in [Figure 6.a](#). A schedule of study procedures is provided in [Appendix A](#).

Figure 6.a Schematic of Study Design

Note: The Follow-up Contact will be conducted by telephone.

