9.1.8 Sexual Functioning Assessments

9.1.8.1 *CSFQ-14*

The CSFQ-14 is a structured self-reported questionnaire designed to measure illness- and medication-related changes in sexual functioning that consists of 14 items measuring sexual functioning as a total score (14 items) and on the subscales of pleasure (1 item), desire/frequency (2 items), desire/interest (3 items), arousal (3 items), and orgasm (3 items). Two additional items are included in the total score, but do not map to a specific phase of the sexual response cycle. Lower scores are associated with worsened sexual functioning [20]. The subject should complete the CSFQ-14 scale before the PGI-I scale at all post-baseline visits.

9.1.8.2 *PGI-I Scale*

The PGI-I scale is a global self assessment used to rate the response of a subject's condition to therapy or intervention. It consists of one question that asks the subject to rate their current condition compared to how it was prior to beginning treatment on a scale of 1 (very much better) to 7 (very much worse). It was originally developed for assessment in women with stress urinary incontinence [21]. However, due to its lack of specificity for medical conditions, and its sensitivity to change, it has been used for subject self assessment in other conditions. The subject should complete the CSFQ-14 scale before the PGI-I scale at all post-baseline visits.

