13.1.3.3 Additional Analyses

The percentage of subjects meeting criteria for sexual dysfunction (ie, CSFQ-14 total score ≤ 47 for men and ≤ 41 for women) at any 2 consecutive visits (using LOCF) during the double-blind Treatment Period will be analyzed by logistic regression, adjusting for baseline CSFQ-14 total score, sex, and treatment.

Time to sexual dysfunction as assessed by the CSFQ-14 will be analyzed using a Cox model with an exact method to handle ties, with treatment and sex as factors.

CSFQ-14 shift from normal (ie, CSFQ-14 total score > 47 for men and > 41 for women) at Baseline to abnormal (ie, CSFQ-14 total score ≤ 47 for men and ≤ 41 for women), and CSFQ-14 negative responders (decrease from Baseline in CSFQ-14 total score ≥ 3) will be analyzed at all visits by logistic regression, adjusting for baseline CSFQ-14 total score, sex, and treatment.

PGI-I will be analyzed by study visit using ANCOVA and LOCF, with treatment, center, and sex as fixed factors.

C-SSRS will be summarized by study visit for each treatment group using descriptive statistics.

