7.1.3 Definition of Study Day and Study Visit Windows

A windowing convention will be used to determine the analysis value for a given study visit that applies to observed data.

Study Day -1 corresponds to the date of the Baseline visit, ie, the randomization date. Other study days are defined relative to Study Day 1, the date of first double-blind study drug dose. Relative day is calculated as (date of interest – date of first dose +1) for study days on or after the

date of first dose and as (date of interest – date of first dose) for study days prior to the first dose date.

For each visit, a window will be defined such that the lower and upper bounds of each window is generally the midpoint between 2 consecutive study visits. The visit windows and applicable study day ranges are presented below in [Table 7.a](#).

Table 7.a Visit Windows

Nominal Visit Week	Nominal Visit Day	CSFQ-14, PGI-I, C-SSRS	Vital signs	Lab, PE,Weight,	PK
Baseline	-1 (a)	≤1 (b)	≤1	≤1	≤1 (b)
1	7	2 – 10			
2	14	11 – 17	2-24		
3	21	18 – 24			2-24
4	28	25 – 31			25-31
5	35	≥32	≥25	≥2	≥32
7	49				

(a) Baseline day has been defined as Day -1 in keeping with Clinical Data Interchange Consortium standards. There is no Day 0.

(b) No baseline assessment for PGI-I or pharmacokinetic (PK) sampling.

More than 1 result for a parameter may be obtained in a visit window. In such an event, the result with the date closest to the scheduled visit day will be used. In the event of 2 observations equidistant to the scheduled visit day, the later of the observations will be used. Treatment Period Last Visit values will be defined irrespective of falling in a particular window. Hence, the windowed Week 8 value may be different than the Last Visit value.

In general, the baseline value for a variable is defined as the last observation prior to the first dose of double-blind study medication (visit date \leq first dose date), including the screening value, if necessary.

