7.9.5 Additional Endpoints

The percentage of subjects meeting criteria for sexual dysfunction (ie, CSFQ-14 total score ≤ 47 for men and ≤ 41 for women) at any 2 consecutive visits (using LOCF) during the treatment period will be analyzed by logistic regression, adjusting for baseline CSFQ-14 total score, sex, and treatment.

Time to sexual dysfunction as assessed by the CSFQ-14 and time to CSFQ-14 negative response (defined as the decrease from Baseline in CSFQ-14 total score ≥ 3) will be analyzed using a Cox model with an exact method to handle ties, with treatment and sex as factors. The SAS code for the time-to-event analysis will be as follows:

```
proc phreg;
  class treat;
  model T_Sexdys*status_1(0) = treat sex/ ties=exact;
```

The analysis will also be supplemented with plots of Kaplan-Meier estimates of sexual dysfunction.

CSFQ-14 shift from normal (ie, CSFQ-14 total score > 47 for men and > 41 for women) at Baseline to abnormal (ie, CSFQ-14 total score ≤ 47 for men and ≤ 41 for women), and CSFQ-14 negative responders (decrease from Baseline in CSFQ-14 total score ≥ 3) will be analyzed at all visits by logistic regression, adjusting for baseline CSFQ-14 total score, sex, and treatment.

PGI-I will be analyzed by study visit using ANCOVA and LOCF, with treatment, center, and sex as fixed factors. MMRM analysis will also be performed.

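### The PGI-I ANCOVA names no covariate; adding baseline CSFQ-14 total score is a free improvement that may gain some precision

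*Protocol*

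**What the plan says.** The PGI-I model is given in the same words in Protocol 2.0 (Additional Analyses), Protocol 13.1.3.3 and SAP 7.9.5: "PGI-I will be analyzed by study visit using ANCOVA and LOCF, with treatment, center, and sex as fixed factors". The SAP then adds that "MMRM analysis will also be performed", without listing the terms of that model.

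Other models in the plan compare as follows:

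- The CSFQ-14 total-score ANCOVA is fitted "with treatment, center, and sex as fixed factors, and baseline CSFQ-14 total score as covariate".
- Sexual dysfunction, shift to abnormal and negative response are analyzed by "logistic regression, adjusting for baseline CSFQ-14 total score, sex, and treatment".
- The only MMRM written out (SAP 7.9.3, for CSFQ-14 change) carries baseline and baseline-by-week.
- Time to sexual dysfunction is analyzed "using a Cox model with an exact method to handle ties, with treatment and sex as factors", so baseline CSFQ-14 is absent there too.

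On the scale itself, the footnote to the visit-window table in SAP 7.1.3 states: "No baseline assessment for PGI-I or pharmacokinetic (PK) sampling". Protocol 9.1.8 describes the item as asking subjects to "rate their current condition compared to how it was prior to beginning treatment".

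**The concern.** A model with three classification factors and no continuous covariate is an ANOVA, whatever it is called. Either the label is wrong or a covariate was intended and not written down. The scale's own baseline cannot be the missing term, because none is collected. The obvious candidate is baseline CSFQ-14 total score. Inclusion criterion 8 requires that score at the Baseline Visit, so every eligible subject has one, and it describes sexual functioning at the time the PGI-I asks subjects to look back to.

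If baseline CSFQ-14 predicts PGI-I after treatment, center and sex are accounted for, leaving it out makes the standard errors of the PGI-I ANCOVA contrasts larger than they need be. A chance difference between arms in baseline sexual functioning would also go unadjusted.

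The MMRM has a separate gap. A programmer who follows the SAP 7.9.3 template for PGI-I meets a baseline term that does not exist for this scale, and must either drop it or substitute another variable. Two programmers could fit different models.

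**Working it through.** **Plan's own figure.** The documents give no SD, effect or power for the PGI-I. The only power statement is for CSFQ-14 change (Protocol 13.3, SAP 6.0): 88 per arm, difference 4.0, SD 8.5, 2-sided 0.025. The noncentrality is 4.0 / (8.5 × √(2/88)) = 3.12. Power is 81.1% by the normal approximation and 80.4% by the noncentral t with 174 df, against the stated 80% or more. Simulating Holm-Bonferroni with a shared paroxetine arm and both true differences 4.0 gives 85.3% per dose, against the stated approximately 85%. Both figures reproduce, and this point does not affect them.

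**Terms side by side.**

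| Model | Treatment | Center | Sex | Baseline CSFQ-14 |
|---|---|---|---|---|
| CSFQ-14 total-score ANCOVA | yes | yes | yes | yes |
| CSFQ-14 MMRM | yes | yes | yes | yes, also by week |
| Logistic models | yes | no | yes | yes |
| Cox model | yes | no | yes | no |
| PGI-I ANCOVA | yes | yes | yes | no |
| PGI-I MMRM | terms not listed | | | |

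**Cost of the covariate.** Take 352 subjects, 4 arms, 2 sexes and 15 centers. The center count is an assumption: the protocol says approximately 15, and SAP 7.1.4 allows pooling of small ones. Residual df without the covariate = 352 − (1 + 3 + 14 + 1) = 333; with it, 332. If the covariate is useless, the df loss costs 333/332 − 1 = 0.3% of variance. Allowing also for chance imbalance in the covariate, 333/332 × (1 + 1/331) = 1.006, that is 0.6% of variance or about 0.3% of the SE.

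**Possible gain.** Let ρ be the partial correlation of baseline CSFQ-14 with PGI-I given treatment, center and sex. Then, before the small cost above:

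- SE ratio = √(1 − ρ²)
- equivalent subjects per arm = 88 / (1 − ρ²)
- power of a contrast assumed to have 80% unadjusted, 2-sided 0.05 = Φ(2.802/√(1 − ρ²) − 1.960)

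The documents do not give ρ, so the values are assumed.

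| ρ | SE ratio | SE smaller by | Equivalent n for 88 | Power from 80% |
|---|---|---|---|---|
| 0 | 1.000 | 0% | 88.0 | 80.0% |
| 0.1 | 0.995 | 0.5% | 88.9 | 80.4% |
| 0.2 | 0.980 | 2.0% | 91.7 | 81.6% |
| 0.3 | 0.954 | 4.6% | 96.7 | 83.6% |
| 0.4 | 0.917 | 8.3% | 104.8 | 86.4% |

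With the 0.6% cost included, break-even is where 1 − ρ² = 1/1.006, so ρ is about 0.08. Below that the loss is negligible; above it there is a net gain.

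**The case against.** The strongest reply is that the benefit is unproven. The relevant quantity is the partial correlation. Sex is already in the model, eligibility truncates baseline CSFQ-14 from below (above 47 for men, above 41 for women), and the PGI-I already rates change from the pretreatment state. CSFQ-14 change contains the measured baseline by subtraction, so a correlation with baseline is to be expected there; the PGI-I is not computed from it. Protocol 9.1.8.2 also stresses that the PGI-I is not specific to a condition. All of this stands, and it argues for the lower end of the range. It does not argue against the covariate, whose cost is negligible even at a correlation of zero.

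A second reply is that the omission may be deliberate. The note to the logistic code in SAP 7.9.4 defines baseline as that of the corresponding response variable, and the PGI-I has none. That is a possible reading, but then the model should be called an ANOVA and the intention stated.

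Three stronger readings are tempting, and the documents do not support them:

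- A reader might infer that precision is certainly lost. That needs a nonzero partial correlation, which is not given.
- A reader might infer that every PGI-I contrast is affected. The PGI-I MMRM terms are unlisted, so it cannot be said that baseline CSFQ-14 is missing there.
- A reader might infer that the PGI-I ANCOVA is the only model without this baseline. The Cox model omits it too, although its outcome is defined by the CSFQ-14.

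**Conclusion.** The point holds as a specification gap with a possible loss of precision. The PGI-I ANCOVA names no covariate and omits the baseline score used in the CSFQ-14 total-score ANCOVAs and the logistic models. Under randomization the planned test is valid and the treatment comparison unbiased. A chance baseline imbalance would be visible, because SAP 7.5 presents baseline CSFQ-14 by arm, but this model would not adjust for it.

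The gain from adding the covariate runs from nothing to about 8% of the SE for partial correlations of 0 to 0.4, and is under 5% up to 0.3. These figures rest on the assumed correlations, full enrollment of 352 and 15 centers.

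The weight is minor. The PGI-I is an additional endpoint with no power claim, SAP 7.1.2 leaves it outside multiplicity control, and the primary analysis and sample size are unaffected.

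**What to change.** Before unblinding, in SAP 7.9.5:

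1. Keep the PGI-I sentence as it stands, including LOCF, and append baseline CSFQ-14 total score as a covariate, so that its terms match those of the primary model.
2. List the terms of the PGI-I MMRM: treatment, center, sex, week, treatment-by-week, baseline CSFQ-14 total score and its interaction with week, following the CSFQ-14 MMRM in SAP 7.9.3.

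Make the matching edit in Protocol 2.0 and 13.1.3.3 only if the protocol is being amended anyway. Otherwise state in the SAP that the covariate is an addition to the protocol model. If the sponsor prefers no covariate, call the model an ANOVA, say that none is intended, and still list the MMRM terms.

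Cost: one phrase and one model term for the ANCOVA, a list of terms for the MMRM, and about one residual degree of freedom. No new data are needed and no other analysis changes. Settling it before unblinding also removes any later choice of covariate.
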